- The second mechanism involves stimulating mechanical receptors on the skin, sending impulses to the central nervous system via tactile stimulation. It has been reported that the resulting impulse provides stimulation/inhibition and neuromuscular re-education(5).
- Moreover, it is argued that the activated gate control mechanism due to these sensory stimuli, along with the release of fascia through space enlargement, increased circulation, and mechanical support, reduces pain(6).

In light of all this information, it is hypothesized that a non-pharmacological approach using a home exercise program (HEP) (spinal extensor strengthening, posture, and balance exercises) and the Kinesio Taping technique in AS patients may achieve reduced pain symptoms, correction of postural deformities, and an increase in respiratory capacity.

REFERENCES

4. Uçkun A, Sezer İ. Ankilozan spondilit ve denge. *Eurasian Journal of Medicine*. 2017;49(3):207-10

RESEARCH PROTOCOL

Document Code:
EY. FR. 16

Revision Date: 24.03.2023

Revision No: 03

Version No: 01

Page No: 3 / 5

3. OBJECTIVE OF THE RESEARCH:

The aim of this study is to investigate the effect of Kinesio Taping on pain, posture, balance, and respiration in ankylosing spondylitis and to demonstrate the difference between this technique and routine home exercises provided to this group of patients.

4. EXPECTED BENEFITS OF THE RESEARCH:

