Investigation of the efficacy of the KT method on pain, posture, balance, and respiration in AS patients.

5. RESEARCH METHODOLOGY:

Participants:

Eighty patients aged 18–65, diagnosed with ankylosing spondylitis, not in the acute flare period, who applied to the Physical Medicine and Rehabilitation (PMR) outpatient clinic of Bursa Yuksek Ihtisas Training and Research Hospital between April 1, 2023, and January 1, 2024, will be included in the study.

- Inclusion Criteria: Patients over 18 years old diagnosed with ankylosing spondylitis
- Exclusion Criteria: Patients with active malignancy, active cellulitis and skin infection, open wounds, deep vein thrombosis, and patients with vestibular and orthopedic pathologies affecting balance.

Intervention:

- Group 2: Will receive only a home exercise program (HEP: spinal extensor strengthening, posture, balance, and respiratory exercises) for 5 weeks, 5 days a week, 3 sets of 10 repetitions.
- Group 1: Will receive the home exercise program in addition to Kinesio Taping applied by a physician to

BURSA YUKSEK İHTİSAS TRAINING AND RESEARCH HOSPITAL

RESEARCH PROTOCOL

Document Code:
EY. FR. 16

Revision Date: 24.03.2023

Revision No: 03

Version No: 01

Page No: 4 / 5

the thoracic, lumbar, and cervical regions in the hospital setting. The KT will remain on the patient for 5 days and then be removed by the patient. The tape will be applied once a week for 5 weeks.

Outcome Measures:

At the end of the 5 weeks, the following will be used for patient assessment: VAS, Range of Motion (ROM), BASMI, BASFI, BASDAI, fingertip-to-floor distance, modified Schober test, chest expansion, AS quality of life questionnaire, and Berg Balance Scale.

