6. DATA COLLECTION TOOLS

- Information-Questionnaire Form
- Self-administered Questionnaire
- Questionnaire administered under observation
- Interviewer-administered Questionnaire
- Observation
- Laboratory examination
- Record from archives
- Other (Specify): ROM measurement with a goniometer will be conducted in the outpatient clinic setting. Fingertip-to-floor distance, chest expansion, and modified Schober measurement will be taken with a tape measure.

NOTE: Please also submit a detailed list of where the required information/laboratory tests will be obtained, along with the pre-authorization letters from the clinics and laboratories.

7. STATISTICAL METHODS FOR DATA ANALYSIS:

- Data analysis will be performed using the IBM SPSS 22.0 statistical software package.
- In addition to descriptive statistical methods (frequency, percentage, mean, standard deviation, median, min-max), the Chi-Square (χ²) test will be used for comparing qualitative data.
- The suitability of the data for normal distribution will be evaluated using the Kolmogorov-Smirnov and Shapiro-Wilk tests.

T.C. Sağlık Bakanlığı
Türkiye Kamu
Hastaneleri Kurumu

BURSA YUKSEK İHTİSAS TRAINING AND RESEARCH HOSPITAL

RESEARCH PROTOCOL

Document Code:
EY. FR. 16

Revision Date: 24.03.2023

Revision No: 03

Version No: 01

Page No: 5 / 5

- If correlation analysis is performed, the Spearman test will be used when the data does not show normal distribution, and the Pearson test will be used when it does.
- For intergroup analysis, the Independent T-test will be applied if normal distribution is detected, and the Kruskal-Wallis test will be applied if abnormal distribution is detected.
- Probability values (P) less than 0.05 will be accepted as significant, indicating a difference between the groups, while values greater than 0.05 will be considered non-significant, indicating no difference between the groups.

8. PLANNED DURATION OF THE RESEARCH:

- Planned Start Date: 01/05/2023
- Planned End Date: 01/01/2024

9. CONTACT PERSON FOR THE RESEARCH:

- Name Surname: [name]
- [contact]
- Date: 07/03/2023

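### Section 7 takes P above 0.05 as proof that the groups do not differ, and no between-group difference with a confidence interval is planned

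*Combined protocol and SAP*

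**What the plan says.** Section 7 (statistical methods) gives one two-sided reading of the P value. The first half is: "Probability values (P) less than 0.05 will be accepted as significant, indicating a difference between the groups". The second half says that "values greater than 0.05 will be considered non-significant, indicating no difference between the groups".

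The tests to which this applies are in the same section: "For intergroup analysis, the Independent T-test will be applied if normal distribution is detected", and otherwise "the Kruskal-Wallis test will be applied if abnormal distribution is detected". Chi-square is named for qualitative data. The other planned output is "descriptive statistical methods (frequency, percentage, mean, standard deviation, median, min-max". No between-group difference, confidence interval, equivalence margin or smallest important difference appears anywhere in the document.

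Two other sections matter. Section 3 states the aim as "to demonstrate the difference between this technique and routine home exercises". Section 5 lists ten outcome measures ("VAS, Range of Motion (ROM), BASMI, BASFI, BASDAI, fingertip-to-floor distance, modified Schober test, chest expansion", then the AS quality of life questionnaire and the Berg Balance Scale) and a total of 80 patients, with no power calculation, allocation ratio or dropout allowance.

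**The concern.** The sentence makes two claims about P above 0.05. The label non-significant is right. The added inference, that the groups do not differ, does not follow from a test of difference. A large P value can come from a narrow interval around zero or from a wide interval that still contains worthwhile effects, and the P value alone does not say which.

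The rule is written as the general one for between-group results, so it would govern the conclusions on pain, posture, balance and respiration alike. What else the plan commits to reporting does not reliably correct it. For t-tested outcomes a reader can derive an interval from the group means, SDs and sizes. For rank-tested outcomes the median, range and P value do not determine one. At stake is a report that says taping makes no difference on outcomes where the data would not support that.

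**Working it through.** **Inputs from the documents.** 80 patients in two groups, threshold 0.05, ten measures.

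**Assumptions not in the documents.** Equal arms (40 each), two-sided testing, normal data, and 0%, 10% or 20% loss (40, 36 or 32 analysed per arm). The 0.5 SD and 0.8 SD thresholds are illustrative. The plan has no figure of its own to reproduce here, because the 80 is stated without design inputs.

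**1. Width of the interval.** The 95% half-width in SD units is t(0.975, 2n−2) × √(2/n).
- n = 40: 1.991 × √(2/40) = 0.445 SD
- n = 36: 1.994 × √(2/36) = 0.470 SD
- n = 32: 1.999 × √(2/32) = 0.500 SD

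An observed difference of zero at 40 per arm thus leaves −0.445 to +0.445 SD plausible. A result at exactly P = 0.05 has an interval from 0 to 2 × 0.445 = 0.89 SD.

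**2. How often a non-significant result supports the label.** Simulation with a true effect of zero (2,000,000 trials), taking the share of results with P above 0.05 whose whole 95% interval lies inside ±m:

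| Analysed per arm | m = 0.5 SD | m = 0.8 SD |
|---|---|---|
| 40 | 21% | 93% |
| 36 | 13% | 88% |
| 32 | 6% | 81% |

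A rough check by the normal approximation at 40 per arm: the standard error is √(2/40) = 0.2236 and the half-width 0.438. For m = 0.5 the observed difference must lie within 0.5 − 0.438 = 0.062 of zero. That has probability 0.218, and 0.218/0.95 = 23%, close to the simulated 21%, which also allows for estimating the SD.

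**3. Over the ten measures.** Count one score per measure and no true effect on any. Expectations add without assuming independence, so 10 × 0.95 = 9.5 measures would be labelled as showing no difference.
- 40 per arm: about 2.0 of the 9.5 exclude 0.5 SD in both directions and 7.5 do not; at 0.8 SD about 8.8 do and 0.7 do not.
- 36 per arm: about 1.2 and 8.3 at 0.5 SD; about 8.3 and 1.2 at 0.8 SD.

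**4. Rank-tested outcomes.** A constructed example on a 0–10 scale, 40 per arm, with the same 40 values in both groups so that P = 1.0. Both groups always have median 5, minimum 0 and maximum 10.
- One value at each extreme and 38 evenly spaced over 5 ± 1: Hodges-Lehmann 95% interval −0.32 to 0.32.
- One value at each extreme and 38 evenly spaced over 5 ± 4: −1.30 to 1.30.
- With mean 5.0 and SD 1.70 also matched, two layouts still give −0.34 to 0.34 and −0.70 to 0.70. The first has two values at each extreme and 36 over 5 ± 1. The second has one at each extreme and 38 spread to give the same SD.

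The example shows only that the planned summaries do not fix the interval. It does not show how often this matters in these data.

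**5. Context: chance of P above 0.05 when an effect exists.** At 40 per arm, on one outcome, from the noncentral t distribution: 74% for a true 0.3 SD, 40% for 0.5 SD and 6% for 0.8 SD. This rate comes from the sample size and better wording does not change it.

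**The case against.** The strongest reply is that the clause is loose shorthand with little practical effect. The sentence first gives the correct label. The aim is to show a difference, so a null result simply fails to support taping, and nothing in the plan depends on an equivalence claim. The missing interval is silence in a five-page protocol, and it can be recovered for t-tested outcomes. The numbers depend on a threshold that the documents do not supply: going from 0.5 to 0.8 SD moves the share of well-supported nulls from 21% to 93%. In the zero-effect scenario used for that count, the no-difference statement is actually true.

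Some of this stands. When the true effect is zero, the conclusion is unsupported rather than false. The size depends heavily on the threshold, which is why both are shown. The unrecoverable gap is limited to rank-tested outcomes, whose number is unknown.

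The core is untouched. The clause is the plan's only rule for reading a P value above 0.05, no other section softens it, and its literal meaning is invalid whatever threshold is chosen. Where a real moderate effect exists, the same rule would state something false.

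**Conclusion.** The concern holds. The inference is invalid as written, and that needs no numerical assumption. Its size does. Under the stated assumptions, most non-significant results would not rule out a moderate effect of 0.5 SD, while most would rule out a large one of 0.8 SD. The problem is therefore serious if moderate effects matter to the investigators and minor if only large ones do; the documents do not say which. It should be fixed, since it affects what is concluded and reported, but it does not affect the conduct of the trial or its test results.

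**What to change.** In Section 7, delete the clause that equates P above 0.05 with the absence of a difference, and write instead:

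> P above 0.05 will be reported as no statistically significant difference detected and will not be taken as evidence that the groups are the same. For each continuous or score outcome the between-group difference will be reported with its 95% confidence interval (mean difference with the t-test, Hodges-Lehmann difference with the rank test). Conclusions will state which effects, in both directions, the interval leaves plausible. Absence of an important difference will be claimed only for an outcome whose important difference was fixed before the data were seen and whose interval excludes it in both directions.

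**Cost.** A few sentences, and one small extra analysis step for rank-tested outcomes. Little precision is lost: in simulated normal data at 40 per arm the Hodges-Lehmann half-width is about 0.45 to 0.46 SD, against 0.445 SD for the t interval.

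**Downsides.** The Hodges-Lehmann difference reads as a shift only if the two distributions have a similar shape. Many null results will have to be called inconclusive. An important difference must be fixed in advance, but only for outcomes on which the investigators want to claim there is none.
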